# 5.11.2 Visit 3: Follow-Up Visit (either 4 – week post laser therapy for Group 1 or 10-week after the baseline for Group 2)

The following procedures and data collection will take place at study visit 3.

- Physical Exam for completing HN-LEF Grading Criteria
- Digital photographs of face and neck
- Symptom burden assessments (HN-LEF Symptom Inventory and NDI)
- Functional status (jaw/neck/shoulder range of motion)
- Quality of life status (EORTC QLQ-H&N35)

# 5.11.3 Visit 4: Follow-Up Visit (either 8 – week post laser therapy for Group 1 or 14-week after the baseline for Group 2)

The following procedures and data collection will take place at study visit 4.

- Physical Exam for completing HN-LEF Grading Criteria
- Digital photographs of face and neck
- Modified Patterson Scale
- Symptom burden assessments (HN-LEF Symptom Inventory and NDI)
- Functional status (jaw/neck/shoulder range of motion)
- Quality of life status (EORTC QLQ-H&N35)
- Blood sample (10 cytokines)

# 5.11.4 Visit 5: Follow-Up Visit (End of Laser Therapy- Group 2 only)

The following procedures and data collection will take place at study visit 5.

- Physical Exam for completing HN-LEF Grading Criteria
- Digital photographs of face and neck
- Symptom burden assessments (HN-LEF Symptom Inventory and NDI)
- Functional status (jaw/neck/shoulder range of motion)
- Quality of life status (EORTC QLQ-H&N35)

# 5.11.5 Visit 6: Follow-Up Visit (4 – Week post laser therapy – Group 2 only)

The following procedures and data collection will take place at study visit 6.

- Physical Exam for completing HN-LEF Grading Criteria
- Digital photographs of face and neck
- Symptom burden assessments (HN-LEF Symptom Inventory and NDI)
- Functional status (jaw/neck/shoulder range of motion)
- Quality of life status (EORTC QLQ-H&N35)

### 5.11.6 Visit 7: Follow-Up Visit (8 – Week post laser therapy– Group 2 only)

The following procedures and data collection will take place at study visit 7.

- Physical Exam for completing HN-LEF Grading Criteria
- Digital photographs of face and neck
- Modified Patterson Scale
- Symptom burden assessments (HN-LEF Symptom Inventory and NDI)
- Functional status (jaw/neck/shoulder range of motion)
- Quality of life status (EORTC QLQ-H&N35)
- Blood sample (10 cytokines)

### 5.12 Subject Withdrawal

Subjects may withdraw from the study at any time without impact on their care. They may be discontinued from the study at the discretion of PI [name], due to lost follow-up or adverse events. Subjects may also be withdrawn by PI [name] from the study given safety consideration.

### 6 Statistical Plan and Statistical Analysis

While this study is a preliminary study of efficacy and effect sizes, a maximum alpha level of 0.05 will be used for the statistical tests.

Aim 1 and Aim 2: Preliminary Efficacy of the Intervention. All of the measures used for estimates of efficacy are continuous in scale. Mixed effects and generalized estimating equation (GEE) models, with the generalized linear modeling framework with the appropriate link function for the nature of the specific

outcome variable being analyzed, will be used to generate estimates of the effect of the intervention on the severity of lymphedema, symptom burden, function status, and QOL.

**Exploratory Aim**: Inflammatory Biomarkers. Inflammatory biomarkers will be analyzed using methods identical to those described for aims 1 and 2.

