# 3.1.2 Allocation to Interventional Group

After completion of baseline measures, participants will be randomized via a computer-generated, permuted block program, conducted by Co-I Statistician [name], to one of 2 arms: Group 1 (laser therapy) and Group 2 (wait-list control). Randomization will be stratified by lymphedema laterality (unilateral vs. bilateral) with a 1:1 allocation, which will allow us to balance potentially important subgroups equally among the two groups.

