### 3.1.3 Study Intervention Phase and Follow Up Phase

Group 1 (laser group): After completion of the baseline measures, Group 1 participants will be scheduled for LLLT. The LLLT includes receiving LLLT twice a week for 6 weeks (12 sessions). After completion of the 12-sessions of LLLT, participants will be given a) contact information and instructions to call for problems and b) a calendar outlining dates for the 4- and 8-week post-LLLT follow-up data collection. Group 1 participants will need to complete 4 study assessment visits.

Group 2 (wait-list control group): After completion of the baseline measures, Group 2 participants will not undergo the LLLT therapy but will complete all the same study assessments as the laser therapy group, including the baseline, 6-week after the baseline, 10-week and 14-week after the baseline assessments. After the 14-week baseline assessment, they will be offered the same LLLT sessions as the laser group. After completion of the 12-sessions of LLLT, participants will undergo the 4- and 8-week post-laser follow-up data collection. Group 2 participants will need to complete 7 study assessment visits.

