### 4.5 Total Number of Subjects and Sites

Total number of subjects: 40

Total number of subjects was determined with consideration for an estimated 20% attrition rate. Single-site study: Subjects will be enrolled at Penn only.

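### Section 6 gives no small-sample method for GEE or mixed models on 32 to 40 participants; default GEE tests would exceed the stated 0.05 maximum

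*Combined protocol and SAP*

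**What the plan says.** Section 6 (Statistical Plan and Statistical Analysis) names the model families for Aims 1 and 2: "Mixed effects and generalized estimating equation (GEE) models, with the generalized linear modeling framework with the appropriate link function". It applies the same methods to the inflammatory biomarkers, and states that "All of the measures used for estimates of efficacy are continuous in scale". On error control it says that "a maximum alpha level of 0.05 will be used for the statistical tests", in a sentence that opens "While this study is a preliminary study of efficacy and effect sizes".

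Section 4.5 gives the size: "Total number of subjects: 40", and "Total number of subjects was determined with consideration for an estimated 20% attrition rate". Section 3.1.2 adds: "Randomization will be stratified by lymphedema laterality (unilateral vs. bilateral) with a 1:1 allocation". Section 3.1.3 sets the assessments in the controlled period, "including the baseline, 6-week after the baseline, 10-week and 14-week after the baseline assessments".

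Section 6 does not say which model serves which outcome. It names no primary contrast, working correlation, covariance structure, standard-error estimator, reference distribution, degrees-of-freedom method or small-sample correction.

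**The concern.** The participant is the independent unit, so a GEE analysis here has 32 to 40 clusters. The ordinary sandwich variance is a large-sample estimator. With this few clusters it is biased downward, and a z or chi-square reference ignores the uncertainty in the estimated variance. Both errors make tests reject too often and intervals too short. Mixed models tested against z or chi-square share the second problem.

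An analyst could therefore follow Section 6 to the letter, use software defaults for GEE, and exceed the alpha that the same section calls a maximum. Sections 2 and 12 make preliminary efficacy the main objective and intend the data for designing a later RCT. Overstated precision would carry into that design.

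**Working it through.** **Inputs from the documents.** N = 40 and 20% attrition (Section 4.5); 1:1 allocation (3.1.2); baseline plus three later assessments (3.1.3); alpha 0.05 and continuous outcomes (6).

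**Assumed, because the documents do not say.** Two-sided tests; Gaussian outcomes; within-person correlation exchangeable 0.5 or 0.7, or AR(1) 0.7; complete data for those analysed.

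**The plan's own figures.** 40 × (1 − 0.20) = 32, or 16 per arm, and 32 / 0.80 = 40, so the attrition arithmetic is consistent. Alpha is declared, and no effect size, SD or power is given, so there is nothing further to reproduce.

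**Closed form for uncorrected GEE.** Take an arm-by-visit model with m participants per arm. The sandwich variance of a change-from-baseline contrast is (m − 1)/m times the unbiased variance. Rejecting at |z| > 1.96 is then the same as |t| > 1.96 × √((m − 1)/m) on 2m − 2 df.

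- m = 20: 1.96 × √(19/20) = 1.910; 2P(t₃₈ > 1.910) = 0.064
- m = 16: 1.96 × √(15/16) = 1.898; 2P(t₃₀ > 1.898) = 0.067

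The joint 3-df Wald test has critical value 7.815. By Hotelling's result it rejects when F(3, 2m − 4) > 7.815 × ((m − 1)/m) × (2m − 4)/(3(2m − 2)).

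- m = 20: 7.815 × 0.95 × 36/114 = 2.344; P(F₃,₃₆ > 2.344) = 0.089
- m = 16: 7.815 × 0.9375 × 28/90 = 2.279; P(F₃,₂₈ > 2.279) = 0.101

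Interval width relative to a correct t interval: 1.910/2.024 = 0.944 at 40 participants and 1.898/2.042 = 0.929 at 32. The intervals are about 6% and 7% too narrow.

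**Simulation under no effect** (40,000 trials per setting, four visits, all three correlation patterns; Monte Carlo SE about 0.1-0.15 percentage points):

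| Test | 20/20 | 16/16 or 14/18 |
|---|---|---|
| GEE uncorrected, one contrast, z | 6.4-6.5% | 6.7-6.9% |
| GEE uncorrected, joint 3 df, chi-square | 8.9-9.0% | 10.0-10.5% |
| GEE bias-corrected, one contrast, t | 5.1% | 4.9-5.2% |
| GEE bias-corrected, joint 3 df, F | 4.9-5.0% | 4.9-5.2% |
| REML random intercept (covariance correct), one contrast, z | 5.3-5.4% | 5.3-5.4% |
| REML unstructured, one contrast, z | 5.8-5.9% | 5.9-6.0% |
| REML unstructured, joint 3 df, chi-square | 7.7-7.8% | 8.3-8.7% |
| REML unstructured, one contrast, t(n − 2) | 5.1% | 4.9-5.1% |

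The bias correction in the table multiplies the sandwich by m/(m − 1), which is what Kauermann-Carroll gives in this model.

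**Sensitivity.**

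- Fitted GEE adjusted for a two-level stratum (2,000 trials, SE about 0.6 points): 7.2% and 7.6% for one contrast, 8.7% and 9.2% for the joint test, at 20 and 16 per arm.
- Baseline-adjusted GEE (6,000 trials, correlation 0.6): 6.4-6.9% at 20 per arm; at 16 per arm, 7.5% for one visit and 7.8-8.0% for the visit average. With Mancl-DeRouen and a t or F reference it gave 3.9-4.5%.
- One skewed (lognormal) setting at 16 per arm: 6.1% for one contrast and 8.5% for the joint test, uncorrected.

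**The case against.** The strongest reply is that Section 6 names model families and nothing more. REML with Kenward-Roger, or GEE with a corrected sandwich, fits within its words. A reader might infer that the plan has adopted large-sample tests and that its alpha is therefore already 6.5-10.5%. The documents do not support that; the excess depends on an analyst's choice that they leave open. This part of the reply stands.

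A reader might also apply the whole 6.5-10.5% range to both model families. That is wrong for a single contrast from a mixed model, the first method named, where the excess is at most about one point if the covariance is right. A random-intercept model fitted to AR(1) data rejected about 11.8% of the time, but that is covariance misspecification, a separate fault that a small-sample correction does not cure.

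Two further points reduce the size. The upper end of the range needs a joint group-by-visit test that Section 6 does not name. And 32 is the low end of the cluster count, because participants with partial follow-up still contribute to these models.

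Finally, this is a pilot: Section 12 takes completed recruitment and data collection as its key benchmark, no decision is tied to a p-value, and Section 6 promises estimates without mentioning intervals. That lowers the stakes. It does not remove the point, because Section 6 still sets a maximum alpha and nothing in it ensures that the maximum is kept.

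**Conclusion.** The concern holds in conditional form. If GEE is used with uncorrected sandwich errors and a z or chi-square reference, type I error is about 6.5-7.5% for one LLLT versus wait-list contrast and about 9-10.5% for a joint 3-df test, with 95% intervals about 6-7% too narrow. A correctly specified REML mixed model with a z reference gives about 5.3-6.0% for one contrast. An unstructured mixed model with a joint chi-square test gives about 7.7-8.7%, so choosing a mixed model without a degrees-of-freedom rule does not fully settle the matter.

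The figures rest on Gaussian outcomes, correlation of about 0.5-0.7 and 32 to 40 analysed participants. The closed-form values do not depend on the correlation, and the direction was the same in every setting tried. The exact size should be read as approximate: skewness lowered it, and covariate adjustment at 16 per arm raised it to as much as 8.0%.

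Severity is moderate. In a pilot, an excess of 1.5 to 2.5 points on a single contrast does not make the change a precondition for going ahead.

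**What to change.** Add to Section 6, for the primary, secondary and biomarker outcomes alike:

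- Mixed models are fitted by REML and tested with Kenward-Roger or Satterthwaite degrees of freedom.
- Any GEE analysis uses a bias-corrected sandwich variance (for example Kauermann-Carroll or Mancl-DeRouen) with a t or F reference.

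Either route is adequate. Mancl-DeRouen is slightly conservative here (3.9-4.5%), while the Kauermann-Carroll type correction returned about 5%. The same edit is a good place to name the primary model, its covariance structure and the primary contrast, since the correction only has a definite meaning once those are fixed.

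The cost is one or two sentences, standard software options and slightly wider intervals. No extra participants, visits or data are needed.

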# 7 Safety and Adverse Events

### 8.1 Safety Monitoring

The following strategies will be in place to monitor the safety of participants during the course of the study.

During the course of this study, study staff will monitor any adverse side effects or events when interacting with participants and be trained to report these to the PI's immediately. Common Terminology Criteria for Adverse Events (CTCAE v5.0) will be used to document adverse events of the trial. All of the staff members who are involved in this study will be trained by the PI [name] on how to use CTCAE v5.0.

In addition, participants in this study will be screened against the inclusion and exclusion criteria. Participants will be educated regarding signs and symptoms related to adverse events (e.g., sudden increase in swelling) requiring urgent or emergent medical care.

### 8.2 Recording of Adverse Events

During each contact with the subject, the trained staff will seek information on adverse events by specific questioning and, as appropriate, by examination. Information on all adverse events will be recorded immediately in the source document, and also in the appropriate adverse event module of the case report form (CRF). All clearly related signs, symptoms, and abnormal diagnostic procedures results should be recorded in the source document.

All adverse events will be reviewed by PI [name] and Study Physicians [name] (Co-Is), and the Medical Monitor, [name] (see 8.6 Medical Monitoring section), any contributing factors will be reviewed, and strategies to prevent further complications will be developed and implemented. [name] will meet with the study staff monthly to evaluate any other safety concerns. Adverse events will be reported to the Penn IRB within the window required by the IRB. If the study staff identify the following unanticipated problems related to the research (e.g., infection in the treated area, sudden increase in swelling), which occur during the study, Drs. [name], [name], and study lymphedema therapists, as well as the Medical Monitor, [name], will be notified immediately. Patients will be referred and receive appropriate and timely treatment. [name] and [name] will determine if participants with adverse events or any unexpected issues will remain on the study based on safety considerations. [name] and [name] as well as the Medical Monitor, [name], will evaluate the relationship of each adverse event to the study procedures. [name], [name], and the Medical Monitor, [name], will make the determination of the relationship of the adverse event to the study procedures (e.g., definitely related, probably related, possibly related, unlikely or unrelated).

The clinical course of each event will be followed until resolution, stabilization, or until it has been determined that the study intervention or participation is not the cause. Serious adverse events that are still ongoing at the end of the study period will be followed up to determine the final outcome. Any serious adverse event that occurs after the study period and is considered to be possibly related to the study intervention or study participation will be recorded and reported immediately.

# 8.3 Reporting of Adverse Events, Adverse Device Effects and Unanticipated Problems to Penn IRB and ACC

PI [name] and the study team will conform to the adverse event reporting timelines and formats, per the Penn IRB reporting requirements and Abramson Cancer Center reporting guidelines.

Low-Level Laser Therapy in Head and Neck Chronic Lymphedema Version: 9-12-2022

The following information will be included at the time of the initial report:

• Study identifier

Subject number

Date of onset

A description of the event

• Study site

•

- Current status
- Whether study intervention was discontinued
- The reason why the event is classified as adverse events
- Investigator assessment of the association between the event and study intervention

Additionally, all other events (unanticipated problems, adverse reactions, unanticipated adverse device effects and subject complaints) will be recorded and reported with respect to Penn policies as described in the Penn Manual.

# 8.3.1 Investigator reporting: notifying the study sponsor

Not applicable. The study has no external sponsor.

### 8.4 Unblinding Procedures

Not applicable.

### 8.5 Stopping Rules

We do not anticipate significant adverse events. Given no safety data available in the population under study, the research may involve risks that are currently unforeseeable. If any one event is identified that may have caused any type of harm to a participant, study recruitment and associated study activities will be immediately halted until the Medical Monitor, [name], and the study team review the event and determine if any study procedures need to be revised. Study recruitment and associated study activities will only resume after review of the study protocol has been completed and any recommended revisions made as advised by both the Medical Monitor, [name], and the Penn IRB.

### 8.6 Medical Monitoring

[name] has agreed to be the Medical Monitor for the proposed project. This person is not directly involved in the trial and is not collaborating with the investigators in any other trials. In this role, [name] will review all AEs including grading, toxicity assignments, and all other safety data and activity data observed in the trial. [name] may recommend reporting of adverse events and relevant safety data not previously reported and may recommend suspension or termination of the trial.

### 8.6.1 Data and Safety Monitoring Plan

The data and safety monitoring plan will adhere to policy guidance and standards set by the Penn IRB. The PI [name] will be responsible for monitoring the entire study. The Medical Monitor, [name], will provide oversight for this trial.

Data Management: 1) Self-reported questionnaires will be completed by participants using a tablet to enter their responses into REDCap. The research assistant will review participants' completeness for each questionnaire. If participants prefer, or if there are technical difficulties, hard copy forms will be used. All hard copy data will be double-entered into REDCap, checked for discrepancies, and reconciled with hard copy forms. All forms will be stored in a secured cabinet. 2) Physical examination data collected by the study staff will be entered by the research assistant into REDCap. These data will also be double-entered, checked for discrepancies, and reconciled with the hard copy form. 3) Imaging data (digital photos) will be deidentified (white-out eyes) and only scoring data will transfer out to REDCap. Data from various sources will be integrated into the study databases by the Data Specialist. All data will be coded without any identifiable information. The PI [name] and the data specialist will monitor and ensure that all data are timely entered into the databases and all protocol specifics are met. PI [name] will monitor all databases monthly and maintain a master table that links participants to ID numbers in a password-protected database on a secure server throughout the study and after the close of the study.

Monitoring by the PI: PI [name], with assistance from the Co-Is [name], the study lymphedema therapists, and other study staff members, will monitor all of the study activities to ensure safety of participants and integrity of the data collection and management. The research team will meet monthly to discuss recruitment, retention, study progress, and any safety concerns. Any potential issues related to the study activities will be discussed and addressed appropriately and timely. Participants will be educated regarding signs and symptoms related to adverse events requiring urgent or emergent medical care. All adverse events will be documented using CTCAE criteria, reviewed by [name], [name], and the Medical Monitor, [name]. Any contributing factors will be reviewed. Strategies to prevent further complications will be developed and implemented. Although adverse events are highly unlikely, should they develop, they will be reported to the Medical Monitor immediately and to the Penn IRB within the required time window.

# 8.7 Data Safety Monitoring Board

Not applicable.

### 8 Study Administration, Data Handling and Record Keeping

### 8.1 Confidentiality

All of the study data will be stored in a secured network drive managed by University of Pennsylvania School of Nursing IT staff member. All participants will be assigned a study ID number (e.g., 300). Numbers will be assigned by trained study staff. It is important and necessary for the study team to know participants' names in order to communicate with them during the study. This information will be maintained in a participant tracking database that is not stored on the hard drive, accessible only to the study team members through a password protected computer, and linked to a Penn School of Nursing server that is accessible only the study team. The name column will be deleted at the end of the study.

# 8.2 Data Collection and Management

Data collection will be conducted by a trained staff member in a private room at the Abramson Cancer Center (ACC) HNC clinics (participant recruitment) and at the Penn Nursing Biobehavioral Lab (baseline and follow-up data collection, as well as the low-level laser therapy). The following procedure will be utilized to protect the privacy of the research participant. All data will be coded and filed without any names or other identifiable information. Self-reported questionnaires will be completed by participants using an encrypted and secured tablet to enter their responses into REDCap. The research assistant will review participants' completeness for each questionnaire. If participants prefer, or if there are technical difficulties, hard copy forms will be used. All hard copy data will be double-entered into REDCap, checked for discrepancies, and reconciled with hard copy forms. All hard copies will be placed in a locking file cabinet. Only the study team has access to the file cabinet and electronic database. After the study is concluded, the research data will be stored at Penn School of Nursing.

